8.4 Investigational Product Accountability

The pharmacist or any other appropriate health professional, who is designated by the Investigator, will be responsible for recording the receipt and administration/dispensing of all Investigational Product supplies as well as for the storage and allocation of these supplies. Investigational Product supplies should be counted by the Site Monitor during monitoring visits.

In accordance with the applicable regulations, the Investigator and/or other appropriate designated worker will keep an inventory of all clinical trial material (CTM) received. All used and unused CTM will be accounted for in an Inventory Form provided to the Investigator by the Site Monitor. CTM inventory forms will be examined and reconciled by the operator ([name]) at the end of the study.

A copy of the completed Inventory Form will be retained in the Investigator's study file, and a copy will be filed in the Sponsor's Trial Master File.

These records should include dates, quantities, batch/serial numbers, expiry dates, and the Investigational Product and study patients. Investigators should maintain records that document adequately that the patients were provided with the Investigational Products specified by the protocol.

8.5 Destruction / Retrieval of Surplus Investigational Products

The site monitor will be responsible for the retrieval of used and surplus / unused Investigational Product. In all cases, an Investigational Product accountability form will be completed.

8.6 Concomitant Therapy

No concomitant therapy will be prohibited by the current protocol.

9 STUDY SCHEDULE

9.1 Flow chart

Tasks	Visits	Screening/baseline	Follow-up
		Day 1	Day 90
Patient information and informed consent signature		X	
Inclusion/exclusion criteria		X	
Randomization		X	
Investigational device supply		X	
Plaque Control Record (PCR)		X	X
Inflammation assessment (BoP)		X	X
Gingival recession assessment (REC)		X	X
Pocket depth probing (PD)		X	X
Gingival abrasion (GA)		X	X
Gingival coloring variation assessment		X	X
Dental photograph		X	X
Oral hygiene instructions		X	
Investigational device collection			X
Assessment of toothbrush usage (patient reported)			X
Assessment of toothbrush usage (brush wear assessment)			X
Adverse events collection			X

Figure 2: Flow chart of the course of the study.

9.2 Investigators' meeting and Calibration

Before starting the study, the examiners / operators will be trained and calibrated to implement an identical procedure. Every member of the investigation team is a former trainee of the European post graduate program in periodontics, which should ensure homogenization of periodontal measurements, thereby limiting the investigator's bias.

9.3 Procedures at Each Visit

Study procedures are described in the tabular overview provided in Section 6.2.

A maximum of 2 visits will be scheduled as follows:

- Screening/Baseline visit at Day 1 (D1), with baseline oral assessment in case of inclusion
- Follow-up visit: at 90 days

Screening/Baseline Visit (Day 1):

This initial study phase consists of a pre-screening of the patients. During routine visits, possible patients will be selected. The patients will be informed on the background of the study and a written explanation will be given concerning the objectives and the study procedures. They all will request to give their written consent prior to enrolment into the study.

The following procedures will apply:

- Explanation to the patient of the purpose of the study and planned oral hygiene procedures;
- Inclusion/Non-Inclusion criteria;
- Patient agreement to comply with study requirements and informed consent form signing;
- Randomization;
- Supply of the Investigational Product (by the operator);
- Plaque measurement (PI);
- Inflammation assessment (BOP);
- Gingival recession assessment (REC);
- Pocket depth probing (PD);
- Dental Photographs and analyze of Gingival macro relief coloring (GA);
- Tooth brushing session;
- Oral Hygiene Instructions.

Subsequent visit date will be scheduled at the end of this visit.

Follow-up visit at 90 Days

The following procedures will apply:

- Plaque measurement (PI)
- Inflammation assessment (BOP);
- Gingival recession assessment (REC);
- Pocket depth probing (PD);
- Dental Photographs and analyze of Gingival macro relief coloring (GA);
- Dental photograph;
- Toothbrush collection (by the operator);
- Assessment of toothbrush usage (patient reported);
- Assessment of toothbrush usage (brush head wear assessment);

- Assessment of toothpaste usage (paste weighed)
- Adverse events collection.

9.4 Assessment of Compliance.

Upon completion of clinical assessments, all manual toothbrushes as well as all brush heads will be collected by the operator, and the age of the brush or brush head will be assessed by asking the participants the number of weeks the brush or brush head was used. After completion of the study, the operator will assess all manual toothbrushes as well as all brush heads for brush wear according to the method described by Conforti *et al.* on a 0–4 scale (Conforti *et al.*, 2003).

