Methodology	
This is a randomized, monocentric, examiner-blind, two-arm, parallel, controlled clinical research study. It aims to assess gingival abrasion by the comparison of pre- to post-brushing after a single brushing and after 12 weeks of daily home brushing using a macro-relief scoring based on photographs of the gingiva. The study also aims to assess plaque removal, gingival inflammation, gingival recession and gingival color after 12 weeks. To enter the study, adult male and female subjects attending the service of dentistry at Rothschild hospital (Paris, France) will refrain from all oral hygiene procedures for 24 hours. Subjects will have the study procedure explained to them both orally and by written instructions. Eligible patients will give their written consent to participate before being included into the study. Following a baseline clinical examination for collection of the following periodontal parameters: plaque control record (PCR), bleeding on probing (BOP), gingival recession (REC), and probing pocket depths (PD), the subjects will be randomized into two balanced groups, test group assigned to the Sonicare ProtectiveClean® HX6848/92 with C2 Optimal Plaque Defense head HX9022/10 (electric toothbrush) and control group assigned to the Pierre Fabre Inava 20/100, a reference manual toothbrush. Subjects will be instructed to brush their teeth for one minute under supervision with their assigned toothbrush and a sodium monofluorophosphate (1450 ppm F) toothpaste (elmex® SENSITIVE PROFESSIONAL) with a low level of abrasion to minimize bias due to toothpaste abrasivity. After brushing, they will again be evaluated for primary and secondary outcomes (post-brushing). Subjects will be dismissed from the study site with their assigned toothbrush and toothpaste, and instructed to brush twice daily at home for the next 12 weeks. The subjects will be instructed to brush for two minutes during each tooth brushing. The subjects will report to the study site after 12 weeks of product use, at which time

Confidential

	they will be re-evaluated for gingival abrasion, as well as for plaque removal, gingival inflammation, gingival recession and gingival color. Data (photographs and clinical measurements) will be collected, i.e. primary and secondary variables of each patient, by blinded examiners.
Number of patients	30 per group, 60 in total
Visits	1. Inclusion (D1) 2. Follow-up (D90)

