Eligibility criteria	
Inclusion criteria
 
 1. Dentate males and females must be at least 18 years and not more than 75 years of age 2. Patient able to understand and sign the informed consent prior to starting the study 3. Patient with a minimum of 3 teeth in each of the 4 quadrants and no/or pockets >4 mm 4. Ability and willingness to comply with all study requirements. 
Non-inclusion criteria
 
 1. Pregnancy 2. Patient with cervical restorations 3. Current smoker 4. Patient with orthodontic banding 5. Patient with oral lesions or periodontal diseases 6. Patient who has been deprived of his/her freedom by administrative or legal decision or who is under trusteeship/guardianship 7. Patient already using an electric toothbrush 8. Patient with conditions or circumstances, which may prevent completion of study participation or interfere with analysis of study results, such as history of non-compliance, or unreliability; 9. Patient with non-plaque induced gingival diseases or localized gingival ulceration 10. Thin gingival phenotype 11. Patients with cardiac pacemakers to prevent any interference between the power toothbrush and the implantable cardiac device.
Method of administration	
After screening, clinical examination, informed consent collection and randomization, a blinded examiner will provide each patient a manual toothbrush or a sonic toothbrush depending on his/her allocation group (control or test group).
 
The examiner will orally explain the appropriate tooth brushing technique, the frequency and duration of tooth brushing (twice a day, 2 mins). Each participant will receive a tube of sodium monofluorophosphate (1450 ppm F) toothpaste (elmex® SENSITIVE PROFESSIONAL).
 
At the end of the study, each patient will give back the used toothbrushes and tubes of toothpaste to the blinded examiner.

Treatment scheme	
Visit 1 (V1): (D0) screening, patient's information on the study protocol, inclusion, randomization, baseline oral measurements, supply of investigational device, oral hygiene instructions, and dental photographs.
 
Visit 2 (V2): (D90) Collection and verification of investigational device, oral measurements and dental photographs.

Study Duration	Inclusion period: 6 Months

Confidential

	Total study duration: 9 Months
Study Schedule	Q2 2021 – Q1 2022

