6.5 Blinding /Unblinding

At first the eligible patients are randomized. After this step, the data for each patient of two groups (test and control) are collected. The examiner, laboratory and statistical procedures will be blind to the treatment.

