7.2 Eligibility Criteria

The volunteers will be informed on the background of the study and a written explanation will be given concerning the objectives and the involvement methods. They all will request to give their written consent prior the enrolment into the study.

Each patient entering the study must comply with all of the primary inclusion criteria and will be excluded if one or more exclusion criteria is met.

7.2.1 *Inclusion Criteria*

1. Dentate males and females must be at least 18 years and not more than 75 years of age
2. Patient able to understand and sign the informed consent prior to starting the study
3. Patient with a minimum of 3 teeth in each of the 4 quadrants and no/or pockets >4 mm
4. Ability and willingness to comply with all study requirements.

7.2.2 *Non-inclusion Criteria*

1. Pregnancy
2. Patient with cervical restorations
3. Current smoker
4. Patient with orthodontic banding
5. Patient with oral lesions or periodontal diseases
6. Patient who has been deprived of his/her freedom by administrative or legal decision or who is under trusteeship/guardianship
7. Patient already using an electric toothbrush
8. Patient with conditions or circumstances, which may prevent completion of study participation or interfere with analysis of study results, such as history of non-compliance, or unreliability;
9. Patient with non-plaque induced gingival diseases or localized gingival ulceration
10. Thin gingival phenotype
11. Patients with cardiac pacemakers to prevent any interference between the power toothbrush and the implantable cardiac device.

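### The protocol gives conflicting Day 1 orders for randomisation, brush supply and baseline measurement, so chairside baselines and the pocket check may follow allocation

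*Protocol*

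**What the plan says.** Section 6.5 gives a sequence in words: "At first the eligible patients are randomized. After this step, the data for each patient of two groups (test and control) are collected". It does not mention handing over the brush.

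Section 9.3 lists the Day 1 procedures with randomisation, then "Supply of the Investigational Product (by the operator", then plaque, bleeding, recession, pocket depth and photographs, then the brushing session. It introduces the visit as one "with baseline oral assessment in case of inclusion". The flow charts in the synopsis and in 9.1 list randomisation and device supply above the measurements.

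The synopsis speaks with more than one voice:
- Methodology: "Following a baseline clinical examination for collection of the following periodontal parameters" (plaque, bleeding, recession, pocket depth), "the subjects will be randomized into two balanced groups".
- Treatment scheme: "inclusion, randomization, baseline oral measurements, supply of investigational device".
- The Method of administration row gives a third account: "After screening, clinical examination, informed consent collection and randomization, a blinded examiner will provide each patient a manual toothbrush or a sonic toothbrush".

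Inclusion criterion 3 in section 7.2 reads "Patient with a minimum of 3 teeth in each of the 4 quadrants and no/or pockets >4 mm". Section 6.4 allots a randomisation number only once screening has found the patient eligible. Sections 6.1, 6.3 and 6.5 state that the examiner is blind.

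**The concern.** A baseline should be fixed before allocation, so that nothing about the assigned arm can reach it. Here the baseline does several jobs. It is the reference for change to Day 90. Under section 11.1 it is also tested for imbalance between arms, and it becomes the ANCOVA covariate if imbalance is seen. A baseline influenced by knowledge of the arm could therefore affect the covariate and also which analysis is run.

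Plaque, bleeding, recession and pocket depth are judged live at the chair. If the patient already has a sonic or a manual brush, the examiner's blinding is the main safeguard.

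Eligibility raises a related question. However the pocket wording of criterion 3 is read, it cannot be verified without probing. If the only probing comes after randomisation, the protocol does not show how that part of eligibility is established beforehand.

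**Working it through.** The point concerns order, so the check is to set the places side by side.

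| Place | Randomisation and baseline | Brush supply |
|---|---|---|
| 6.5 | Randomise, then collect data | Not mentioned |
| 9.3, Day 1 list | Randomisation above all measurements | Between randomisation and measurements, by the operator |
| Flow chart, synopsis | Randomisation above all measurements | Above the measurements, no person named |
| Flow chart, 9.1 | Same | Same |
| Synopsis, Treatment scheme | Randomisation, then baseline | After baseline |
| Synopsis, Methodology | Baseline examination, then randomisation | No separate step; brushing with the assigned brush follows randomisation |
| Synopsis, Method of administration | Clinical examination before randomisation | After randomisation, by a blinded examiner |

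1. **Randomisation.** Five places put it before the baseline measurements and two put it after the examination. The split runs through the synopsis as well as between the synopsis and the body.

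2. **Supply.** Three places (9.3 and the two flow charts) list it before the measurements. The Treatment scheme and the Method of administration put it after measurement or examination.

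3. **Who supplies.** Section 9.3 names the operator. The Method of administration names the blinded examiner, who also explains the technique and takes back the brush at the end. Section 8.3 gives a different technique for each arm, so whoever instructs the patient knows the arm. This cannot be squared with 6.3, where the examiner is kept uninformed at every stage of measurement.

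4. **Combined effect.** No single passage has the examiner hand out the brush before the baseline. The Method of administration, read alone, protects the Day 1 baseline but not what the same examiner measures afterwards. The baseline is exposed if a site takes the order from 9.3 and the person from the Method of administration, and nothing in the protocol rules that out.

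5. **Which outcomes.** Plaque, bleeding, recession and pocket depth are chairside measures and are exposed. The primary abrasion score is read from photographs by blinded observers, with scoring delayed (5.1.2, 11.5). Colour is also extracted from photographs in a blinded manner (11.6). An unused brush in the patient's possession does not alter the photographed gingiva.

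6. **Eligibility.** Section 7.1 requires consent before any screening assessment. In 9.3 no measurement lies between consent and randomisation, and pocket depth comes later. Sections 6.4 and 6.5 nevertheless assume that eligibility is already settled.

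7. **Figures.** None depends on this point. The sample size reproduces: n = 2(z₁ + z₂)² × SD²/difference², with SD²/difference² = 0.84²/0.67² = 1.572. At 80% power, 2 × (1.960 + 0.842)² × 1.572 = 24.7, so 25 per group. At 90%, 2 × (1.960 + 1.282)² × 1.572 = 33.04, so 34 per group. Both match 11.8.

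**The case against.** The strongest reply is that 9.3 and the flow charts are lists with no stated rule of sequence. Read as strict chronology, 9.3 would breach the protocol elsewhere. It places the eligibility criteria before consent signing, against 7.1. It also has one photograph item, before brushing, although the synopsis and 6.6 call for an assessment immediately afterwards. The Method of administration is no better as a chronology, since it names the examination before consent. This stands as a reason not to over-read any one list. It does not remove the conflict, because 6.5 states its order in words and the Methodology states the reverse.

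A second reply is that the baselines precede supervised brushing in both 9.3 and the Methodology, and the examiner is declared blind. The first part stands: the brush cannot have changed the tissue. The second part is weakened by the Method of administration.

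Several stronger readings are tempting, and the documents do not support them:
- A reader might infer that 6.5 also hands over the brush first. It is silent on supply.
- A reader might set the body against a uniform synopsis. The Treatment scheme also randomises before baseline.
- A reader might infer that ineligible patients will be randomised and then removed by staff who know the arm. Sections 6.4 and 6.5 require eligibility first, 9.3 describes pre-screening during routine visits, and 11.3 has no rule expressly removing such patients from the full analysis set. No failure rate for the pocket criterion is given, so a count would be invented.
- A reader might express the bias as a share of the 0.67 difference in 11.8. That difference belongs to the photograph score, the outcome least exposed.
- A reader might take ANCOVA as the planned analysis. Section 11.1 uses it only if imbalance is observed.

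**Conclusion.** The contradiction on Day 1 order is real and should be resolved. Under the 6.5/9.3 order, the chairside baselines of up to all 60 planned patients are taken after allocation, with examiner blinding as their main protection. The protocol contradicts itself on that blinding by giving brush supply both to the operator and to the blinded examiner. The primary score is much less exposed.

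On eligibility the finding is narrow. The protocol requires eligibility before randomisation, but lists the only scheduled probing that could verify criterion 3 after it.

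The size of any bias cannot be derived from the documents, and no sample-size figure changes. The conclusion assumes that a site could reasonably follow 6.5 and 9.3 as written. The study diagram in 6.2, to which 9.3 refers, is not reproduced in the text at hand. If it shows an order, that would be one more statement to align and would not remove the conflict.

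**What to change.** State one Day 1 order and use it in the synopsis (Methodology, Method of administration, Treatment scheme and flow chart), in 6.5, in the 9.1 flow chart and in 9.3:

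1. Consent.
2. Eligibility, including pocket probing.
3. Baseline measurements and pre-brushing photographs, recorded.
4. Randomisation.
5. Brush supply by the operator, out of the examiner's sight.
6. Supervised brushing.
7. Post-brushing photographs.

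Say in 9.3 that the list is a sequence. In the Method of administration, move brush supply, technique instruction and brush collection from the blinded examiner to the operator, so that it agrees with 9.3 and 6.3.

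The cost is wording only. The protocol already places these steps on Day 1, so no visit or measurement is added.

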6.2 Study Design

[figure not shown]

Figure 2: Study diagram

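### Section 9.3 lists periodontal probing before the photographs scored for gingival abrasion at both visits, and no visible text reverses this, so probe-induced signs could enter the primary score

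*Protocol*

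**What the plan says.** **Visit lists.** Both visit lists in Protocol 9.3 run plaque, BOP, recession, pocket depth, and then "Dental Photographs and analyze of Gingival macro relief coloring (GA". At Day 1 the brushing session comes after the photographs.

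**Other listings.** The flow charts in the synopsis and in 9.1 place the BOP and pocket-depth rows above the abrasion, coloring and photograph rows. The synopsis treatment scheme for Visit 1 names "baseline oral measurements, supply of investigational device, oral hygiene instructions, and dental photographs", and for Visit 2 it again names oral measurements ahead of photographs.

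**Day 1 narrative.** The synopsis methodology is the only visible text with an explicit sequence: "Following a baseline clinical examination for collection of the following periodontal parameters: plaque control record (PCR), bleeding on probing (BOP", recession and pocket depth come first, then randomization and supervised brushing. It continues: "After brushing, they will again be evaluated for primary and secondary outcomes (post-brushing".

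**Score and sites.** The synopsis and 11.5 define the primary score from photographs as five items of 0 to 3 points: erythema, inflammation, bleeding, recession and erosion. Under 5.1.1 it is recorded on the buccal aspects of teeth 6, 4, 3 and 1 in each quadrant. Under 5.2.2.4 bleeding is assessed by marginal probing, with inflammation sites on all teeth. Under 5.2.2.2 pocket depth is probed on buccal 16, 14, 13 and 11, although the preceding section announces a full-mouth periodontal examination.

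**The concern.** Probing the gingival margin can itself cause redness and bleeding. If the photograph follows, a scorer who sees only the image cannot separate a probing mark from a brushing mark, and blinding to the arm does not help. The probed and scored sites overlap.

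Two things are at stake. Variable probe-induced signs add noise to a trial with about 80% power at 25 evaluable patients per arm. More seriously, BOP is a secondary endpoint on which the arms are compared. If the manual arm bleeds more readily at Day 90, it would also show more probe-induced bleeding in its Day 90 photographs. Part of a secondary effect would then be counted as abrasion, in favor of the test brush.

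**Working it through.** **1. Which listings can be read as a time order?**

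- *Flow charts (synopsis, 9.1).* Abrasion is above the photograph row, yet it is scored from photographs. Row order is therefore not chronological.
- *Synopsis, Visit 2.* Device collection is named before the measurements, whereas 9.4 collects brushes once the assessments are complete. Not a reliable sequence.
- *Synopsis, Visit 1.* Hygiene instructions come before the photographs; in 9.3 they come after. Not reliable either.
- *9.3, Day 1.* Randomization precedes the baseline examination, against the synopsis methodology. Eligibility precedes consent signing, against 7.1. Partly contradicted.
- *9.3, Day 90.* No conflict with 9.4 or with the methodology text.
- *Synopsis, week 12.* "they will be re-evaluated for gingival abrasion, as well as for plaque removal, gingival inflammation, gingival recession and gingival color" names abrasion first, but as an outcome and not as a step. It does not set the reverse order.

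The concern therefore rests on 9.3, above all its Day 90 list, and on the absence of any visible text to the contrary.

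**2. The plan's own figure.** From 11.8: difference 0.67, SD 0.84, two-sided 0.05.

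n = 2 × (1.960 + 0.842)² × (0.84/0.67)² = 24.7, so 25 per arm at 80% power. With 1.282 in place of 0.842, n = 33.0, rounded up to 34, at 90%. Both stated figures are reproduced.

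**3. Ceiling.** Three items × 3 points = 9 of the 15 points. This is the range of the scale, not an estimate of bias.

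**4. When does the effect cancel?** Let p be the share of patients with a one-point probe-induced rise, and f the fraction of the patient score affected.

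Shift in the arm difference in change = f × [(p manual, D90 − p manual, D0) − (p sonic, D90 − p sonic, D0)].

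Randomization makes the two baseline shares equal in expectation, which leaves f × (p manual, D90 − p sonic, D90). A simulation with 1,000,000 patients per arm, 30% in both arms at baseline and f = 1, gave differences of −0.001 (D90 30% vs 30%), 0.099 (30% vs 20%) and 0.199 (30% vs 10%).

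**5. Illustrative shifts.** The percentages are assumptions; none is in the documents. f = 1 means the whole score rises; f = 1/4 means one of four averaged quadrants is affected.

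| Arm gap at D90 | f = 1 | share of 0.67 | f = 1/4 | share of 0.67 |
|---|---|---|---|---|
| 10 points | 0.10 | 15% | 0.025 | 4% |
| 20 points | 0.20 | 30% | 0.05 | 7% |
| 33 points | 0.33 | 49% | 0.083 | 12% |

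To move the difference by a tenth of 0.67 (0.067 points), the arms must differ by 0.067/1 = 6.7 percentage points, or by 0.067/0.25 = 26.8.

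**6. Chance of a significant result if the brushes do not truly differ.** SE = 0.84 × √(2/n) = 0.238 at 25 per arm and 0.217 at 30. The smallest significant observed difference is t × SE: 2.011 × 0.238 = 0.48, and 2.002 × 0.217 = 0.43. The rejection rate follows from the noncentral t with noncentrality shift/SE:

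- shift 0.33: noncentrality 1.39 and 1.52, rejection about 28% and 32%
- shift 0.20: noncentrality 0.84 and 0.92, rejection about 13% and 15%

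The nominal rate is 5%.

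**7. Noise alone.** If probing added independent noise with an assumed SD of 0.2 to 0.8 points to the change score, the total SD would be √(0.84² + 0.2²) = 0.86 to √(0.84² + 0.8²) = 1.16. Power at 25 per arm would fall from 0.81 to between 0.78 and 0.53.

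**The case against.** **The protocol never orders a photograph after probing at Day 90.** This stands. The lists are not declared chronological, most of them are contradicted as sequences elsewhere, and 9.3 itself says "Study procedures are described in the tabular overview provided in Section 6.2", where the reader finds "Figure 2: Study diagram", a figure that is not shown. The hospital's standard shooting protocol (5.2.2.1) and the calibration (9.2) might also fix the order. A reader might infer that the protocol prescribes a contaminated measurement, or that six agreeing listings confirm one another. The documents support neither reading. What remains is that the list a site would work from puts probing first, and nothing visible corrects it.

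**Equal handling cancels, and scoring is blinded.** Largely right. The one explicit order, probing before the Day 1 post-brushing evaluation, is harmless between arms. The argument does not cover Day 90 if BOP differs by arm by then.

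**Inflammation and bleeding are in the score by definition.** Also right. Photographing first removes only the probe-induced increment.

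**Moving the Day 1 photograph has a price.** If only the pre-brushing photograph goes ahead of probing, probing falls between it and the post-brushing photograph. The within-arm single-brushing change, which the synopsis names as an aim and 11.1 would test within groups, would then mix probing with brushing. The fix has to deal with this.

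**Conclusion.** The point holds as a should-fix, with medium confidence. Following 9.3 as listed gives a worse primary measurement than the reverse order would, and the order cannot be repaired in analysis once the photographs exist.

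Bias between arms needs three conditions: sites follow the list, probing leaves visible signs in the photographs, and those signs differ by arm at Day 90. None can be established from the documents, which also do not say in what order the preliminary study photographed and probed. The shifts of 0.025 to 0.33 points are illustrations and not estimates.

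Two inferences should be resisted. One is that the primary result is biased by a known amount; no document gives a probing effect or an arm difference in BOP. The other is that, because even 0.33 is below the smallest significant difference (0.43 to 0.48), probing alone could not produce a positive result. That compares an average shift with a critical value and ignores sampling variation. With no true difference, a 0.33 shift would still give a significant result in about 28% to 32% of trials.

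**What to change.** In 9.3 and the synopsis, state that the photographs used for the abrasion and color change from baseline to Day 90 are taken before any periodontal probing at both visits: at Day 1 after consent and before probing and brushing, at Day 90 before the oral measurements. Adjust "with baseline oral assessment in case of inclusion" so that these photographs may precede the pocket-depth eligibility check, and align the Section 6.2 figure if it differs.

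For the Day 1 single-brushing change, keep the pre- and post-brushing photographs on the same side of probing. One way is to repeat the photograph set after baseline probing and just before brushing. Otherwise, limit that change to the comparison between arms. Since the post-brushing evaluation also covers secondary outcomes, its photographs should come before any repeat probing.

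The cost is a few sentences and, with the repeat option, one more photograph set at Day 1. A few consented patients later found ineligible will have been photographed. The definition of the endpoint does not change.

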6 STUDY DESIGN

6.1 Type of study

This will be a monocentric, interventional, reference-controlled, randomized, single blind, and superiority study.

The examiner will be blind regarding the investigational products.

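### Day 90 brush collection is placed after the chairside assessments, and the synopsis has the blinded examiner handle the brushes: an avoidable risk to the blinded scoring of plaque, bleeding and recession

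*Protocol*

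**What the plan says.** **Blinding.** Section 6.1: "The examiner will be blind regarding the investigational products". Section 6.3 adds that the examiner must not learn the brush group at any point in the measurements, and section 6.5 repeats that the examiner is blind.

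**Timing of the Day 90 collection.** Section 9.4: "Upon completion of clinical assessments, all manual toothbrushes as well as all brush heads will be collected by the operator". The Day 90 list in section 9.3 puts plaque, bleeding, recession, probing depth and photographs first, and only then "Toothbrush collection (by the operator". The synopsis treatment scheme words Visit 2 as "Collection and verification of investigational device, oral measurements and dental photographs", so collection is named first there.

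**Who handles the brush.** On Day 1, section 9.3 has "Supply of the Investigational Product (by the operator". The synopsis, under method of administration, says "a blinded examiner will provide each patient a manual toothbrush or a sonic toothbrush depending on his/her allocation group", and then "At the end of the study, each patient will give back the used toothbrushes and tubes of toothpaste to the blinded examiner".

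**The concern.** The trial is single-blind, and its sponsor makes one of the two brushes. Patients know what they were given. Plaque, bleeding and recession are judged live in the mouth, so keeping the examiner unaware of the arm is the main safeguard against biased scoring of those endpoints. A sonic brush and a manual brush cannot be mistaken for each other, and a glimpse of the device or a remark from the patient would disclose the arm.

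Against that background, section 9.4 fixes the one collection time that leaves the device with the patient for the whole Day 90 examination. The synopsis goes further and puts the brushes in the hands of the person who is meant to be blind. If examiners know the arm and have any expectation about it, between-group differences in the chairside endpoints may partly reflect that expectation.

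**Working it through.** No arithmetic applies. The check sets the protocol's own statements side by side.

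**1. When is the brush collected?**

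| Place | Position of collection at Day 90 | Explicit timing? |
|---|---|---|
| 9.4 | after the clinical assessments | yes |
| 9.3, Day 90 list | after the measurements and photographs | list order only |
| Synopsis, treatment scheme | named before measurements and photographs | list order only |
| Flow charts (synopsis and 9.1) | Day 90 | no order within the visit |

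Only 9.4 fixes a sequence.

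**2. Can the synopsis line be read as a sequence?** Its Visit 1 counterpart reads "baseline oral measurements, supply of investigational device, oral hygiene instructions, and dental photographs". It names photographs once, at the end, although the primary endpoint needs photographs both before and after the supervised brushing. That line is not a reliable chronology, so the Visit 2 line should not be treated as one. The two places list collection in different positions, and that is all that can be said. The 9.3 list is itself a weak guide to order, since it names the Day 90 photographs twice.

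**3. Who handles the brush?**

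| Task | Synopsis | 9.3 and 9.4 |
|---|---|---|
| Hand out on Day 1 | blinded examiner | operator |
| Take back at the end | blinded examiner | operator |

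This is an explicit conflict, and the synopsis side is incompatible with 6.1, 6.3 and 6.5. An examiner who hands a patient the allocated brush knows the arm from that moment. The same synopsis paragraph has the examiner explain the brushing technique, and section 8.3 gives a different technique for each brush, so the explanation discloses the arm too.

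**4. Order and person together.**

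- Operator, after the assessments (9.4): the examiner does not handle the device, but the patient still has it during scoring.
- Operator, before the assessments: the device is gone before scoring starts.
- Examiner, after the assessments: the Day 90 scores are already recorded, but handing out the brush on Day 1 has disclosed the arm.
- Examiner, before the assessments: the examiner knows the arm before scoring. This is where the synopsis leads if its list order is followed.

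Moving collection forward without also settling the person could therefore make matters worse than 9.4 as it stands.

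**5. Which endpoints are exposed?** Section 5.2.2 lists four secondary endpoints: colour, plaque, bleeding and recession. Colour is extracted from photographs by blinded observers (11.6). The other three are measured at the chair, so 3 of 4 are exposed. The primary abrasion score is graded from photographs by blinded observers (5.1.2, 11.5).

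**The case against.** The strongest reply is that 9.4 is compatible with the blind. A patient who has not yet handed over a brush has not thereby shown it. No passage puts the device in the examination room or in the examiner's sight, 6.3 forbids informing the examiner, and a separate role does the collecting. Patients could also name their brush aloud whatever the collection time, so reordering closes only one route. On this view the timing is a site-procedure detail.

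Much of that stands. A reader might infer that 9.4 unblinds the examiner; the documents do not show this. A reader might also infer that the synopsis prescribes the reverse order; it does not, because its line carries no sequence words and its Visit 1 companion is not chronological. And a reader might want a false-positive rate attached. The protocol gives neither how often a brush would be seen nor how far a score would move, so any such rate would be purely hypothetical and none is given here.

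Two things survive. First, collection by the operator before the examination removes the device, and collection afterwards does not, so 9.4 fixes the less protective of two equally easy options. The protocol also contains no instruction to patients to keep the brush or its name from the examiner. Second, the conflict over who handles the brush is written in the text and needs no inference.

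**Conclusion.** The point holds as an avoidable weakness in how the blind is protected, together with a plain contradiction over who handles the brushes. The contradiction is the more serious part: followed literally, the synopsis tells the examiner the arm on Day 1.

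The size of any bias is unknown and cannot be estimated from the protocol. Its reach is bounded: plaque, bleeding and recession at Day 90. It would be wrong to conclude that the primary result is compromised, because abrasion is scored from photographs by observers described as blind. That limit assumes that the observers are not told the arm and cannot link a photograph to a patient whose brush they handled or saw. The protocol does not say whether observers and chairside examiners are different people.

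The change is worth making before enrolment, since blinding lost at the chair cannot be restored in the analysis.

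**What to change.** 1. In the synopsis (method of administration and treatment scheme), 9.3 and 9.4, state that the operator, and never the examiner, supplies the brush, gives the brush-specific instructions and takes the products back.
2. In the same places, state that at Day 90 the operator collects brush or brush head, handle and toothpaste, and asks the usage questions, away from the examiner and before any clinical assessment or photograph. Section 9.4 at present names manual brushes and brush heads but not the sonic handle.
3. Instruct patients at Day 1, and again on arrival at Day 90, not to show or name their brush to the examiner.
4. Make the change of person and the change of order together, for the reason given in step 4 of the working.

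The cost is a few reworded lines and one instruction to patients. No visit, staff or data item is added. Brush wear is scored by the operator after the study is complete (9.4), and the paste is weighed from the returned tubes, so earlier collection on the same day loses nothing.
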